10.4.2 Serious adverse events waived from expedited regulatory reporting to regulatory authorities

Not applicable.

10.4.3 General guidelines for reporting adverse events

- All AEs, regardless of seriousness or relationship to IMP/NIMP, spanning from the signature of the ICF form until the end of the study as defined by the protocol for that patient, are to be recorded on the corresponding page(s) or screen(s) of the e-CRF.
- Whenever possible, diagnosis or single syndrome should be reported instead of symptoms. The Investigator should specify the date of onset, intensity, action taken with respect to IMP, corrective treatment/therapy given, additional investigations performed, outcome, and his/her opinion as to whether there is a reasonable possibility that the AE was caused by the IMP or by the study procedure(s).
- The Investigator should take appropriate measures to follow all AEs until clinical recovery is complete and laboratory results have returned to normal, or until progression has been stabilized, or until death, in order to ensure the safety of the patients. This may imply that observations will continue beyond the last planned visit per protocol, and that additional investigations may be requested by the monitoring team up to as noticed by the Sponsor in the protocol and informed consent. At the prespecified study end date, patients who experience an ongoing SAE or an AESI should be followed until resolution, stabilization, or death and related data will be collected.
- When treatment is prematurely discontinued, the patient's observations will continue until the end of the study as defined by the protocol for that patient.
- Laboratory, vital signs are to be recorded as AEs only if:
 - Symptomatic and/or,
 - Requiring either corrective treatment or consultation, and/or,
 - Leading to IMP discontinuation or modification of dosing, and/or,
 - Fulfilling a seriousness criterion, and/or,
 - Defined as an AESI.

In this protocol, symptoms and signs of exacerbation or worsening of the disease under trial will usually be captured in the context of efficacy assessment, and recorded on the relapse module of the e-CRF. Therefore, symptoms, relapses or worsening of MS will not be considered as AEs nor captured on the AE module of the e-CRF unless this event is considered possibly or probably related to the IMP (ie, worsening is not consistent with the anticipated natural progression of the disease) and/or the MS relapse meets the criteria for a serious AE (eg, requires hospitalization). However, for all associated symptoms or events or if an event that was initially considered a possible MS relapse but upon evaluation is found to be any other type of event (some example but not limited to: fever, injury, musculoskeletal event, systemic illness, mood disorder, etc) the event must be captured as an AE/SAE.

Instructions for AE reporting are summarized in [Table 9](#).

10.4.4 Instructions for reporting serious adverse events

In the case of occurrence of an SAE or AESI, the Investigator or any designees must immediately:

- ENTER (within 24 hours) the information related to the SAE or AESI in the appropriate screens of the e-CRF; the system will automatically send a notification to the monitoring team after approval of the Investigator within the e-CRF or after a standard delay.
- There may be instances when copies of medical records for certain cases are requested by the Sponsor. In such case, care should be taken to ensure that the patient's identity is protected and the patient's identifiers in the study are properly mentioned on any copy of a source document provided to the Company. For laboratory results, include the laboratory normal ranges
- All further data updates should be recorded in the e-CRF as appropriate, and further documentation as well as additional information (for laboratory data, concomitant medications, patient status, etc) should be sent (by fax or e-mail) to the monitoring team within 24 hours of knowledge of the SAE or AESI. In addition, every effort should be made to further document any SAE that is fatal or life-threatening within a week (7 days) of the initial notification.
- A back-up plan (using a paper CRF process) is available and should be used when the e-CRF system does not work.

Any SAE brought to the attention of the Investigator at any time after the end of the study for the patient and considered by him/her to be caused by the IMP with a reasonable possibility, should be reported to the monitoring team.

10.4.5 Guidelines for reporting adverse events of special interest

For AESIs, the Sponsor must be informed immediately (ie, within 24 hours), as per SAE notification guidelines described in [Section 10.4.4](#) even if not fulfilling a seriousness criterion, using the screens in the e-CRF.

Instructions for AE reporting are summarized in [Table 9](#).

10.4.6 Guidelines for management of specific laboratory abnormalities

Decision trees for the management of certain laboratory abnormalities by sanofi are provided in [Appendix B](#).

The following laboratory abnormalities should be monitored, documented, and managed according to the related flow chart in protocol appendices.

- Neutropenia.
- Thrombocytopenia.
- ALT increase.
- Acute renal insufficiency.
- Suspicion of rhabdomyolysis.

Table 9 - Summary of adverse event reporting instructions

Event category	Reporting timeframe	Specific events in this category	Case Report Form completion		
			AE form	Safety Complementary Form	Other specific forms
AE (nonSAE, nonAESI)	Routine	Any AE that is not an SAE or AESI	Yes	No	No
SAE (nonAESI or AESI)	Expedited (within 24 hours)	Any AE meeting seriousness criterion per Section 10.4.1.3	Yes	Yes	No
AESI	Expedited (within 24 hours)	Acute hypersensitivity/ anaphylaxis	Yes	Yes	No
		Pregnancy	Yes	Yes	Yes
		Symptomatic overdose	Yes	Yes	No
		ALT \geq 3ULN or \geq 2 baseline	Yes	Yes	Yes
		Autoimmune mediated conditions including but not limited to autoimmune encephalitis, cytopenias, ITP, autoimmune hepatitis, nephropathies including anti-glomerular basement membrane (GBM) disease, thyroid disorders and acquired Hemophilia A Temporally associated* pulmonary alveolar hemorrhage Temporally associated* myocardial ischemia, myocardial infarction Temporally associated* stroke Temporally associated* cervicocephalic arterial dissection (* Temporally associated: 1 to 3 days after the last infusion) HLH, Progressive multifocal leukoencephalopathy (PML) Pneumonitis, Serious infections including serious opportunistic infections (eg, Listeria infections, CMV, EBV), HPV associated with cervical dysplasia Malignancy Thrombotic thrombocytopenic purpura	Yes	Yes	No

Abbreviations: AE: adverse events; AESI: adverse event of special interest; ALT: alanine aminotransferase; IMP: investigational medicinal product; ITP: immune thrombocytopenia; nonSAE: nonserious adverse events.

10.4.7 Guidelines for reporting product complaints (IMP/NIMP/device)

Any defect in the IMP/NIMP/device (alemtuzumab/oral prednisone/prednisolone 1 mg/kg or 50 mg, and H2 antagonist) must be reported as soon as possible by the Investigator to the monitoring team that will complete a product complaint form within required timelines.

Appropriate information (eg, samples, labels or documents like pictures or photocopies) related to product identification and to the potential deficiencies may need to be gathered. The Investigator will assess whether or not the quality issue has to be reported together with an AE or SAE.

10.5 OBLIGATIONS OF THE SPONSOR

Adverse events that are considered expected will be specified by the reference safety information (label).

During the course of the study, the Sponsor will report in an expedited manner:

- All SAEs that are both unexpected and at least reasonably related to the IMP (SUSAR), to the regulatory authorities, independent ethics committee (IECs)/institutional review boards (IRBs) as appropriate and to the Investigators.
- All SAEs that are expected and at least reasonably related to the IMPs to the regulatory authorities, according to local regulations.

The Sponsor will report all safety observations made during the conduct of the trial in the clinical study report.

10.6 SAFETY INSTRUCTIONS

For more information about alemtuzumab, please refer to label.

10.7 ADVERSE EVENTS MONITORING

All events will be managed and reported in compliance with all applicable regulations, and included in the final clinical study report.

11 STATISTICAL CONSIDERATIONS

A SAP will be written and finalized prior to database lock to give guidance to the statistical analysis. It will be in compliance with the International Council for Harmonization (ICH) and Food and Drug Administration's Guidance for Industry: Statistical Principles for Clinical Trials.

The Sponsor or its designee will perform the statistical analysis of the data from this study. The analysis will be performed using the SAS® statistical software system Version 9.1 or higher.

11.1 DETERMINATION OF SAMPLE SIZE

At least 60 patients aged from 10 years to less than 18 years will be screened in this study to account for screen failures, to ensure that at least 50 patients are evaluable. According to the means and variability reported in other paediatric MS studies (17), it was assumed that there is an average of 9 new or enlarging T2 lesions during continuation of prior DMT (Period 1) and an overdispersion parameter of 0.7 for both study periods. Further assuming a conservative within-person correlation of 0.25 for the lesion counts, a 10% dropout rate, and a two-tailed significance level of 0.05, this sample size will provide at least 85% power to detect a 50% reduction in the number of new or enlarging T2 lesions after the first course of alemtuzumab (Period 2) compared to the equal-length Period 1. These sample size calculations were simulated using a correlated, repeated measures negative binomial regression model with GEE with robust variance estimation to account for the within-patient correlation in lesion counts between treatment Period 1 (prior DMT) and Period 2 (alemtuzumab).

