
STATISTICAL CONSIDERATIONS
	
Sample size determination:
 
At least 60 patients will be screened in this study to ensure 50 evaluable patients to receive alemtuzumab treatment. This sample size will provide at least 85% power to detect a 50% reduction in the number of new or enlarging T2 lesions during continuation of prior DMT (Period 1) with their number in an equal period after the first course of alemtuzumab (Period 2), assuming 10% dropout and a two-tailed significance level of 0.05. These sample size calculations were simulated using a correlated repeated measures negative binomial regression model with generalized estimating equations (GEE) with robust variance estimation to account for the within-patient correlation in lesion counts between treatment Period 1 (prior DMT) and Period 2 (alemtuzumab).
 
The sample size calculations also assume an overdispersion parameter of 0.7 for both study periods, which is consistent with the variability reported in other paediatric MS studies.
 
Analysis population:
 
Modified ITT (mITT): The primary analysis will be conducted on the population of patients who have received at least 1 dose of alemtuzumab and also have evaluable data for both Period 1 and Period 2.
 
Safety: Safety and tolerability analyses will be conducted on all patients.
 
Primary analysis:
 
The number of new or enlarging T2 lesions during continuation of prior DMT (Period 1) and in an equal length period after the first course of alemtuzumab treatment (Period 2) will be analyzed and compared using a repeated measures negative binomial regression model with GEE.
 
Analysis of secondary endpoints:
 
 Safety and tolerability will be assessed using descriptive statistics and evaluated in comparison to the adult data for the treatment of MS using alemtuzumab. EDSS (descriptive statistics, eg, percentages of stable/improved/worsened since the end of Period 1). The ARR at Year 2 will be estimated using a negative binomial model with robust variance estimation. The change from baseline in cognitive outcomes will be analyzed descriptively.

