11.3 ANALYSIS POPULATIONS

11.3.1 Modified Intent-to-treat population

Modified Intent-to-treat (mITT): The primary analysis will be conducted on the population of patients who have received at least 1 dose of alemtuzumab and also have evaluable data for both Period 1 and Period 2. The mITT population will be used for the analyses of the primary and secondary efficacy endpoints.

11.3.2 Safety population:

The safety population consists of patients who have received at least 1 dose of alemtuzumab. Safety and tolerability analyses will be conducted on all patients in the safety population. At the first database lock after the last patient has completed efficacy assessments including MRI at end of Period 2, some patients will have follow-up beyond the end of Period 2, all available information will be used for safety and tolerability analyses.

PK: the PK population consists of patients who have received at least 1 dose of alemtuzumab and also have evaluable PK data.

PD: the PD population consists of patients who have received at least 1 dose of alemtuzumab and also have evaluable PD data.

For patient study status, the total number of patients in each of the following categories will be presented in the clinical study report using a flowchart diagram or summary table:

- Screened patients.
- Screened failure patients and reasons for screen failure (if data is available).
- Number and percentage of patients who did not complete prior DMT phase, with corresponding reasons.
- Number and percentage of patients who did not complete Period 2 with alemtuzumab, with corresponding reasons.
- Number and percentage of patients who did not complete safety monitoring phase (will be included in final study report only), with corresponding reasons.

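### Does the overdispersion of 0.7 in the sample size section contradict the stated power of at least 85%?

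*Protocol*

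**What the plan says.** Section 11.1 (Determination of sample size) plans to screen at least 60 patients so that at least 50 are evaluable. The planning inputs are a mean of 9 new or enlarging T2 lesions in Period 1, "an overdispersion parameter of 0.7 for both study periods", a within-person correlation of 0.25 between the counts, 10% dropout and "a two-tailed significance level of 0.05". From these, "this sample size will provide at least 85% power to detect a 50% reduction in the number of new or enlarging T2 lesions". The power came from simulation of a repeated measures negative binomial GEE with robust variance.

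The Clinical Trial Summary repeats the dispersion assumption ("The sample size calculations also assume an overdispersion parameter of 0.7 for both study periods") and the power, without the mean or the correlation.

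Section 11.3.1 limits the primary analysis to patients who received alemtuzumab and "also have evaluable data for both Period 1 and Period 2".

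The protocol does not give the variance function to which 0.7 belongs, nor say whether 45 or 50 patients entered the simulation.

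**The concern.** A negative binomial overdispersion parameter is usually the k in variance = mu + k·mu². On that reading the stated inputs give power near 98%, about 13 points above the quoted figure, and the planned number is roughly twice what 85% requires. On the reciprocal reading, with 50 patients less 10% dropout, power comes out almost exactly at 85%. That looks like a mislabelled parameter, with the assumed dispersion out by a factor of 1.43/0.7 = 2.04.

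The two readings describe designs with very different margins, so a reader who takes 0.7 at face value could think the trial more robust than it is. If k = 0.7 is what was meant, one could also ask why so many children are treated.

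There is a related looseness in the counts. Section 11.1 promises 50 evaluable patients and also assumes 10% dropout, while Section 11.3.1 makes evaluable data in both periods a condition of the primary analysis. If 50 is the number analysed, 50/0.9 = 55.6, so 56 must be treated. That leaves 60 − 56 = 4 of the minimum 60 screened (6.7%) for screen failures and run-in losses.

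**Working it through.** **Inputs** (all from Section 11.1): mu1 = 9; a 50% reduction, so mu2 = 4.5 and |ln 0.5| = 0.693; correlation r = 0.25; two-sided alpha 0.05, so z = 1.96; 50 patients, or 50 × 0.9 = 45 after dropout.

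**Formula.** Per-patient variance of the paired log rate ratio:

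V = (1/mu1 + k) + (1/mu2 + k) − 2r·√[(1/mu1 + k)(1/mu2 + k)]

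SE = √(V/n), and power = Φ(0.693/SE − 1.96).

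**Reproducing the plan's figure: k = 1/0.7 = 1.429**
- The two terms are 0.111 + 1.429 = 1.540 and 0.222 + 1.429 = 1.651.
- V = 3.191 − 0.5 × 1.594 = 2.393.
- n = 45: SE = 0.231, power = Φ(1.046) = 85.2%.
- n = 50: SE = 0.219, power = Φ(1.208) = 88.7%.
- n for 85%: (1.960 + 1.036)² × 2.393 / 0.693² = 44.7.

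**Usual reading: k = 0.7**
- The two terms are 0.811 and 0.922.
- V = 1.733 − 0.5 × 0.865 = 1.301.
- n = 45: SE = 0.170, power = Φ(2.117) = 98.3%.
- n = 50: SE = 0.161, power = Φ(2.337) = 99.0%.
- n for 85%: 24.3.

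**Simulation check.** 20,000 trials per cell, correlated negative binomial counts with count correlation 0.25, robust Wald test.

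| k | n | Formula | Simulation (z) | Simulation (t) |
|---|---|---|---|---|
| 0.7 | 45 | 98.3% | 98.2% | 98.0% |
| 0.7 | 50 | 99.0% | 98.9% | 98.7% |
| 1.43 | 45 | 85.2% | 86.0% | 84.9% |
| 1.43 | 50 | 88.7% | 89.0% | 88.3% |

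The lowest entry, 84.9%, has a simulation standard error of √(0.85 × 0.15/20,000) = 0.25 points, so it cannot be told apart from 85%.

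**Other routes to 85% at k = 0.7, n = 45.** Zero correlation still gives 94.2%. A 40% reduction gives 85.9%. A Period 1 mean of about 1.7, or a correlation of about −0.39, gives 85%. Each of these departs from a stated input.

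**Margin under each reading at n = 45.** The alternative truths are assumptions, not figures from the protocol.

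| Assumed truth | k = 0.7 | k = 1.43 |
|---|---|---|
| Period 1 mean 3, 50% reduction | 93% | 78% |
| Period 1 mean 9, 40% reduction | 86% | 61% |

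**Implied Period 1 SD.** √(9 + 0.7 × 81) = 8.1, or √(9 + 81/0.7) = 11.2.

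**The case for a change.** The strongest case for a change runs as follows. A sample size section exists to show how the number follows from the assumptions, and here a reader cannot trace it. Of the readings tried, only the reciprocal with 45 patients keeps every other stated number and lands on 85%. If that is what was simulated, the design has almost no slack; if k = 0.7 was meant, it has a great deal. Sample size justification belongs in the protocol, so the gap cannot be left to the statistical analysis plan, and clarifying it would cost a sentence.

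The traceability point stands, as does the observation that the reciprocal fits best. The stronger claims do not.
- **Error in the power statement.** The protocol states a minimum, and 98% and 85% both meet it.
- **Error in the 0.7.** The parameterisation is not given. If 0.7 is a size parameter, the number is right and only its label is loose. The study cited as its source is not available here to settle it.
- **85% only through the reciprocal.** This assumes that the design was solved for exactly 85% with exactly 45 patients. The protocol says neither, and the reciprocal reading at 50 gives 88.7%.
- **Needless exposure.** Sections 5.1 and 5.2 list safety, tolerability, pharmacokinetics, pharmacodynamics and antidrug antibodies beside efficacy, and Section 4 ties the design to an agreed paediatric investigation plan. Power for the MRI endpoint is not shown to be the only reason for 50 patients.
- **The 50, 45 and 56 counts.** The Clinical Trial Summary describes the 50 as those who are to receive alemtuzumab, which allows 50 treated and 45 analysed. The squeeze to 4 spare patients depends on the other reading, and 60 is itself a minimum.

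**Conclusion.** No change to the plan follows. The arithmetic behind the concern is right: the inputs give about 98% to 99% power if k = 0.7 and about 85% to 89% if k = 1.43, for 45 to 50 patients. The stated floor of 85% holds across that range, taking the simulated 84.9% at 45 patients with a t reference as equal to 85%.

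What remains is missing detail: the variance function, the number simulated, and a consistent use of the word evaluable. Filling it in would leave enrolment as it is. It would also leave the primary analysis in Section 11.4.2.1 untouched, because that is a negative binomial GEE with a robust covariance matrix and uses no planning dispersion. The test result and its interval will rest on the observed counts whichever value was assumed.

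This rests on the other planning inputs (mean 9, 50% reduction, correlation 0.25) being taken as stated. Anyone who wants to judge the margin against a lower lesion rate or a smaller effect should use k = 1.43 as the cautious case.

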11.2 DISPOSITION OF PATIENTS

Appropriate tracking documents for screening, enrollment and follow-up of patients will be established in each center, as needed and in accordance with local regulations.

Screened patients are defined as any patient who signed the informed consent.

This is an open-label, single-arm, before and after switch study without randomization.

Patients who were screened but did not receive any dose of alemtuzumab will be reported separately, but will not be included in any efficacy or safety population.

11.3 ANALYSIS POPULATIONS

11.3.1 Modified Intent-to-treat population

Modified Intent-to-treat (mITT): The primary analysis will be conducted on the population of patients who have received at least 1 dose of alemtuzumab and also have evaluable data for both Period 1 and Period 2. The mITT population will be used for the analyses of the primary and secondary efficacy endpoints.

11.3.2 Safety population:

The safety population consists of patients who have received at least 1 dose of alemtuzumab. Safety and tolerability analyses will be conducted on all patients in the safety population. At the first database lock after the last patient has completed efficacy assessments including MRI at end of Period 2, some patients will have follow-up beyond the end of Period 2, all available information will be used for safety and tolerability analyses.

PK: the PK population consists of patients who have received at least 1 dose of alemtuzumab and also have evaluable PK data.

PD: the PD population consists of patients who have received at least 1 dose of alemtuzumab and also have evaluable PD data.

For patient study status, the total number of patients in each of the following categories will be presented in the clinical study report using a flowchart diagram or summary table:

- Screened patients.
- Screened failure patients and reasons for screen failure (if data is available).
- Number and percentage of patients who did not complete prior DMT phase, with corresponding reasons.
- Number and percentage of patients who did not complete Period 2 with alemtuzumab, with corresponding reasons.
- Number and percentage of patients who did not complete safety monitoring phase (will be included in final study report only), with corresponding reasons.

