In addition, and for the primary endpoint assessment, two periods have been defined:

- **Period 1:** will occur from M-4 up to M0. A baseline MRI will be performed close to M-4 during the screening period and another at Visit 3. Both MRI will be taken while patients are on their prior DMT. It is important to ensure that these 2 MRI assessments are performed 4 months (± 7 days) apart.
- **Period 2:** will occur from M4 to M8: The MRI performed at the M4 visit will be the baseline MRI for Period 2. A second MRI will be performed after alemtuzumab first course of treatment at M8. It is important to ensure that these 2 MRI assessments are performed 4 months (± 7 days) apart.

These two periods will be compared for the primary endpoint analysis.

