8.8 CONCOMITANT MEDICATION

A concomitant medication is any treatment received by the patient concomitantly to any IMP(s). Concomitant treatments have been detailed for all phases of the study and are not limited to the treatment received with the IMP (treatment phase). Concomitant use of alternative medications (eg, herbal treatments, botanicals, etc) for treatment of MS is discouraged due to concerns of possible interactions with study treatment. Patients should be questioned about their use of such nonprescription therapies, all of which will be listed as concomitant medications.

Prior DMT period

Therapy with disease-modifying MS treatments that the patient is currently being administered (ie, limited to interferons and GA only) will be permitted during the screening and prior DMT Treatment Phase. If the investigator determines that the patient needs to be treated with another DMT, the patient will be discontinued from the study.

Prior DMT will be discontinued 7 days before alemtuzumab first administration. Refer to [Section 6.1](#) for further details.

No concomitant therapy with any other disease-modifying MS treatments either licensed or investigational will be permitted during the screening and prior DMT period.

Concomitant use of systemic corticosteroids for the treatment of MS relapse is allowed during the DMT period.

Alemtuzumab treatment phase

Patients who receive any alemtuzumab treatment will continue study participation even if they do not complete the planned treatment regimen. Patients who discontinue study treatment can continue study participation. If a patient is not willing to continue study participation, all efforts should be made to have the EOTP visit performed by the patient.

No concomitant therapy with any disease-modifying MS treatments either licensed or investigational, including interferons and GA, will be permitted during the alemtuzumab treatment phase. If the investigator determines that the patient needs to be treated with another DMT, the patient will be discontinued from the study.

In addition, no other investigational MS therapy, including investigational symptomatic therapy, will be permitted. Use of live vaccines is specifically prohibited for alemtuzumab-treated patients for the 30 days prior to the first alemtuzumab administration at Month 0 and for the 2 years duration of the alemtuzumab treatment phase of the study.

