9.2.1 Secondary efficacy endpoints

9.2.1.1 Expanded disability status scale

Patient disability will be evaluated using the EDSS ([Appendix D](#)), which has long been considered the standard for assessing disability in patients with MS ([19](#)).

The EDSS is an ordinal clinical rating scale which ranges from 0 (normal neurologic examination) to 10 (death due to MS) in half-point increments. Briefly, the assessing neurologist rates 7 functional systems (pyramidal, cerebellar, brainstem, sensory, bowel and bladder, visual ratings) in conjunction with observations and information concerning the patient's mobility, gait, and use of assistive devices to assign an EDSS score.

EDSS steps 1.0 to 4.5 refer to people with MS who are fully ambulatory, while EDSS steps 5.0 to 9.5 are defined by the impairment to ambulation.

The EDSS will be performed by the neurologist at the following visits: Screening, D-7, M4, M8, M12, M15, M18, M21, M24/at EOTP; every 6 months in Safety Monitoring Phase, and at every relapse visit.

9.2.1.2 Annualized relapse rate at Year 2

Subjects/parents/guardians will be instructed to contact their Investigator immediately should any symptoms suggestive of an MS relapse appear. The subject must be examined as soon as possible, within 7 days from the onset date of the relapse.

Relapses are defined as new or recurrent neurological symptoms not associated with fever or infection, lasting at least 24 hours, and accompanied by new objective neurological findings upon examination by the neurologist and documented by the functional system scores. The subject must have objective signs on the neurologist's examination confirming the event.

New or recurrent symptoms that occur less than 30 days following the onset of a relapse should be considered part of the same relapse. The Investigator can, at his/her discretion, treat the patient with corticosteroids.

Relapses will not be considered as AEs (see AE [Section 10.4.3](#)).

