11.4 STATISTICAL METHODS

Analyses for the primary and secondary efficacy endpoints will be conducted using the mITT population. Analyses for the safety endpoints will be conducted using the safety population. Analyses for the PD endpoints will be conducted using the PD populations. Analyses for the PK endpoints will be conducted using the PK populations. Analyses for the exploratory endpoints will be conducted using the safety population.

In the descriptive analyses, summary statistics for continuous variables will minimally include n, mean, standard deviation (SD), minimum, median, and maximum. For categorical variables, frequencies and percentages will be presented. Graphical displays will be provided as appropriate.

Unless otherwise specified, all baseline values will be defined as the last nonmissing value prior to the first course of alemtuzumab.

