11.4.2 Analyses of efficacy endpoints

Analyses for the primary and secondary efficacy endpoints will be conducted using the mITT population.

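### Relapse rate, EDSS and cognition are analysed only in patients with evaluable MRI data for both periods, although none of them needs a scan

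*Protocol*

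**What the plan says.** Section 11.3.1 defines mITT as patients with at least one dose of alemtuzumab and evaluable data for both periods, and continues: "The mITT population will be used for the analyses of the primary and secondary efficacy endpoints". Section 11.4 repeats the assignment, and so does section 11.4.2: "Analyses for the primary and secondary efficacy endpoints will be conducted using the mITT population".

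Sections 6.1 and 9.1.1.1 set up the two periods for the primary endpoint and bound each by a pair of scans. Period 1 runs from the screening scan to the Visit 3 scan. For Period 2, "The MRI performed at the M4 visit will be the baseline MRI for Period 2", and the M8 scan closes it. The word evaluable is not defined, but in this setting it can hardly mean anything except both scan pairs.

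Other populations are treated differently:

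- **Safety:** all dosed patients (11.3.2).
- **PK and PD:** dosed patients with evaluable data of that same kind (11.3.2).
- **Exploratory T1 lesions and brain volume:** "Analyses for the exploratory endpoints will be conducted using the safety population" (11.4).

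On follow-up, section 8.8 says: "Patients who receive any alemtuzumab treatment will continue study participation even if they do not complete the planned treatment regimen". It also says: "If the investigator determines that the patient needs to be treated with another DMT, the patient will be discontinued from the study".

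**The concern.** Section 9.2 lists ARR at Year 2, EDSS and cognition as secondary efficacy endpoints. None of them depends on MRI, but inclusion in their analysis depends on the MRI data of another endpoint. Meanwhile the exploratory endpoints that do need scans use the wider, all-dosed set. Relapse, EDSS and cognition data collected from dosed patients outside mITT would not enter the efficacy estimates.

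The loss may also be related to outcome. A patient judged to need another DMT leaves the study, possibly before M8, and that decision is probably linked to disease activity. ARR at Year 2 is a single-arm estimate, so no concurrent control offsets such selection. Removing these patients would tend to make the ARR look lower than it is among all treated patients.

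**Working it through.** **Primary endpoint first.** Section 11.1 claims at least 85% power with means 9 and 4.5, overdispersion 0.7, correlation 0.25 and 10% dropout. For a paired log rate ratio, Var = [(1/m1 + k) + (1/m2 + k) - 2ρ√((1/m1 + k)(1/m2 + k))]/n.

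- With 0.7 read as the size parameter (k = 1/0.7 = 1.429) and n = 45: Var = (1.540 + 1.651 - 0.5 × 1.594)/45 = 0.0532, SE = 0.231, and power = Φ(0.693/0.231 - 1.96) = 85.2%.
- With k = 0.7 the power is 98.3%.

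The claim reproduces, and nothing below changes it.

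**How many patients.** The 10% dropout rate in 11.1 does not say how much falls after dosing. If all of it does, 50 dosed give 50 × 0.9 = 45 in mITT (5 lost), or 50 evaluable require 50/0.9, about 56, dosed (6 lost). If every dosed patient has four usable scans, none is lost.

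**ARR.** Let d be the share dropped, t their months of follow-up, and m their relapse rate relative to those kept, who are followed for 24 months. By person-time,

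understatement = 1 - [24(1 - d) + td] / [24(1 - d) + tdm].

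With d = 0.10 and m assumed:

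| Follow-up of dropped patients | m = 1 | m = 2 | m = 3 | m = 4 |
|---|---|---|---|---|
| 4 months | 0% | 1.8% | 3.5% | 5.2% |
| 8 months | 0% | 3.4% | 6.7% | 9.7% |
| 24 months (only a scan lost) | 0% | 9.1% | 16.7% | 23.1% |

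Example (t = 8, m = 4): 1 - (21.6 + 0.8)/(21.6 + 3.2) = 1 - 22.4/24.8 = 9.7%.

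For an assumed ARR of 0.20 in those kept, the all-dosed value for m = 2 to 4 is 0.204-0.211 (t = 4), 0.207-0.221 (t = 8) or 0.220-0.260 (t = 24).

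Section 11.4.2.2 plans a negative binomial model, which weights patients by t/(1 + krt), with t in years. Take r = 0.20 and t = 8 months:

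- k = 0.5, m = 2: weights 1.667 and 0.625, so the all-dosed rate is (1.5 + 0.125)/(1.5 + 0.0625) = 1.04 times the kept rate, an understatement of 3.8%.
- k = 2, m = 4: weights 1.111 and 0.526, ratio (1.0 + 0.2105)/(1.0 + 0.0526) = 1.15, an understatement of 13.0%.

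With equal follow-up (t = 24) the weights cancel and the table stands.

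**Sampling error for comparison.** 45 patients × 2 years × 0.20 = 18 relapses in 90 person-years, with an exact Poisson 95% interval of 0.12 to 0.32.

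**Other endpoints.** Section 9.2.1.1 states: "The EDSS will be performed by the neurologist at the following visits: Screening, D-7, M4, M8, M12, M15, M18, M21, M24/at EOTP". That is 7 post-baseline EDSS assessments to M24. Cognition and quality of life have 5 each (M4, M8, M12, M18, M24). A patient who stays to M24 without one usable scan loses up to all of these. Confidence intervals for means widen by √(50/45) = 1.054, about 5%. If 10% of kept patients worsen on EDSS (assumed), the all-dosed figure is 0.9 × 10% + 0.1 × 10% × m, that is 11-13% for m = 2 to 4.

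**The case against.** **The largest ARR figures have the weakest mechanism.** The 9-23% range needs patients who stay for two years, lose only a scan, and still relapse 2 to 4 times as often. One link exists: section 9.1.1.1 bars MRI within 2 weeks of steroids and wants paired scans 4 months ± 7 days apart, so a treated relapse can disturb a scan date. But a timing rule does not by itself make a patient non-evaluable. This stands; the better supported range is the one for early leavers.

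**Less is recoverable from early leavers.** Section 8.8 says: "If a patient is not willing to continue study participation, all efforts should be made to have the EOTP visit performed by the patient". That covers patients unwilling to continue. It does not clearly cover those discontinued for another DMT, for whom section 10.3.5 asks only for an assessment where possible. A patient who leaves before M8 has one scheduled cognition visit after dosing, M4. This stands too, but relapses and assessments up to leaving are collected in any case.

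**Quality of life is not clearly governed.** Section 9.2 lists it apart from efficacy, and only its place in 11.4.2.2 brings it under the rule. Correct; the firm finding is for ARR, EDSS and cognition.

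**The data are not wholly lost.** Excluded patients remain in the safety population, serious or treatment-related relapses are reported as adverse events (10.4.3), and patients not completing Period 2 are counted with reasons (11.3.2). True, but none of this returns their data to the efficacy estimates.

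**The SAP could add an all-dosed summary.** It could, but three protocol sentences already fix the main population, so this is not an open detail.

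**Conclusion.** The concern holds and is minor. The protocol fixes an MRI-based population for endpoints that need no MRI. Under the 10% dropout rate this affects between 0 and about 6 dosed patients. For early leavers the ARR is understated by about 2-10% on person-time, and by up to about 13% at M8 with strong overdispersion. The 9-23% range applies only if patients who merely miss a scan also relapse more often. If exclusion is unrelated to outcome, there is no bias, only intervals about 5% wider.

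The relapse-rate multipliers, the 0.20 ARR, the dispersion values and the 10% EDSS worsening are all assumptions. Every ARR shift shown lies inside the sampling interval. The primary comparison and its power do not change, and section 11.4.2.3 plans no formal test of secondary endpoints.

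**What to change.** Keep mITT for the primary lesion count and for the proportion of patients with new or enlarging T2 lesions, since both compare the two periods. In sections 11.3.1, 11.4 and 11.4.2, assign ARR, EDSS and cognition to all patients with at least one dose, which is the existing safety population, using all available data. Name the same population for quality of life so that it no longer rests on placement. For ARR, use log follow-up time as the offset. Report the mITT results as a sensitivity analysis.

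The cost is one sentence in each of the three sections, the usual amendment approvals under section 15, and a little more analysis. No new population, visit or data item is needed. The ARR may come out slightly less favourable.
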